3.4. SAFETY ENDPOINTS

- IOP measurements
- Slit-lamp biomicroscopy
- BCVA
- Ophthalmoscopy
- AE monitoring

3.5. DESCRIPTION OF TRIAL DESIGN

This is a Phase 2, multi-center, double-masked, randomized, vehicle-controlled, parallel-group study designed to evaluate the safety and efficacy of KPI-121 0.25% ophthalmic suspension in subjects with inflammatory MGD.

This study will include up to 6 clinic visits, including 2 weeks of single-masked vehicle run-in followed by up to 30 days of investigational product dosing (KPI-121 0.25% ophthalmic suspension or vehicle).

Up to 750 subjects at up to 12 centers located in the United States (US) will be screened at Visit 1 (Screening). Subject meeting eligibility criteria will enter a 14-day run-in period of QID dosing (1-2 drops per eye of single-masked vehicle). Approximately 200 subjects will be randomized to KPI-121 0.25% ophthalmic suspension or vehicle.

At Visit 2, subjects who continue to meet inclusion/exclusion criteria (with the exception of Inclusion Criteria #4 and #7) will be randomized in an approximate 1:1 ratio to either 1) KPI-121 0.25% ophthalmic suspension administered as 1-2 drops in each eye QID for up to 4 weeks or 2) vehicle administered as 1-2 drops in each eye QID for up to 4 weeks.

The study eye will be selected based on the qualification criteria entered into the Interactive Web Response System (IWRS) for stratification at randomization. These scores are based on findings at Visit 1 only. If both eyes qualify for the study, the study eye will be designated as OD. Randomization numbers will be assigned to subjects as they are entered into the IWRS, based on the following 2 stratification criteria:

- Subject's Visit 1 (Day -14) [REDACTED] score [REDACTED]
[REDACTED] AND
- Visit 1 (Day -14) investigator-rated posterior lid margin hyperemia score [REDACTED]

The IWRS will assign masked study kit numbers, and bottles of investigational product will be dispensed at designated visits. The Sponsor, Investigators, and study staff will be masked during the randomization process and throughout the remainder of the study.

Subjects will return to the clinic for complete study evaluations at Visits 4 and 6 (Day 15 \pm 1 day and Day 29 \pm 1 day, respectively). Subjects will also return at Visits 3 and 5 (Day 8 \pm 1 day and Day 22 \pm 1 day, respectively) [REDACTED], evaluate ocular discomfort, and assess concomitant medication use and AEs. Subjects will discontinue dosing and be released from the study at Visit 6 (Day 29 \pm 1 day).

[REDACTED]

A summary of events is provided in [Appendix 1](#). Assessments in this study will include:

- In-clinic subject-rated assessment of ocular discomfort ([Appendix 2](#))
- [REDACTED] severity and frequency assessments ([Appendix 3](#))
- Investigator-rated assessment of posterior lid margin hyperemia ([Appendix 4](#))
- Investigator-rated assessment of the character of the content of meibomian glands ([Appendix 4](#))
- Investigator-rated assessment of expressibility of meibomian glands ([Appendix 4](#))
- Investigator-rated assessment of conjunctival hyperemia ([Appendix 5](#))
- Unanesthetized Schirmer Test ([Appendix 6](#))
- BCVA ([Appendix 7](#))
- Slit lamp biomicroscopy ([Appendix 8](#))
- Corneal fluorescein staining ([Appendix 9](#))
- IOP measurement ([Appendix 10](#))
- Dilated ophthalmoscopy ([Appendix 11](#))
- [REDACTED]
- [REDACTED]
- TFBUT ([Appendix 14](#))

A study schematic follows ([Figure 1](#)).

[figure not shown]

FIGURE 1: STUDY SCHEMATIC

3.5.1. Investigational product

KPI-121 0.25% w/v will be supplied as a suspension in opaque dropper bottles. KPI-121 0.25% ophthalmic suspension is a sterile, aqueous, submicron suspension of LE and will be supplied in a 7.5 mL, white, low-density polyethylene plastic bottle with a white, controlled-drop polyethylene tip and a white polypropylene cap. Each bottle contains 5.5 mL (nominal fill) of drug product.

Subjects randomized to the vehicle control arm will receive the same bottles containing all components at the concentrations used in the KPI-121 0.25% ophthalmic suspension with the exception of the active component, LE.

Subjects will be instructed to shake the investigational product bottle prior to each instillation.

TABLE 2: COMPOSITION OF KPI-121 0.25% (w/v) DRUG PRODUCT

Ingredient	Function	Concentration (% w/v)
Loteprednol etabonate	Active pharmaceutical ingredient	0.25

TABLE 3: COMPOSITION OF VEHICLE

At Visit 1, eligible subjects will receive 2 bottles of single-masked, investigational product from a common site level supply. The bottle labels for the single-masked period contain the following information: sponsor name, protocol number, lot number, storage temperature, and required statement(s) per the appropriate regulatory agency.

The randomized, double-masked, investigational product kit consists of a box containing 3 dropper bottles of investigational product. At Visit 2 (Day 1/Randomization), subjects will receive 2 bottles of double-masked investigational product (KPI-121 0.25% ophthalmic suspension or vehicle) from their assigned kit. At Visit 4 (Day 15 ± 1 day), subjects will receive 1 additional bottle of investigational product from their assigned kit. All bottles will

CONFIDENTIAL

be returned to the site at Visit 6 (Day 29 ± 1 day). The box labels and the dropper bottle labels will contain the following information: sponsor name, protocol number, randomization number, storage temperature, and required statement(s) per the appropriate regulatory agency.

All investigational products will be stored in a secure area with limited access at controlled room temperature (15-25°C/59 -77°F). At Visits 1 and 2, when subjects receive the first dose in the clinic, that dose will count as 1 of their 4 daily doses. Subjects will then self-administer 3 additional doses of investigational product during the remainder of that day to complete QID dosing. All visits should be scheduled in the morning to allow subjects to receive a full day of QID dosing.

Subjects will be asked to instill 1 dose upon awakening and then 3 subsequent doses approximately 4 hours after their previous dose. The 4 doses will be described as “Morning Dose,” “Mid-Morning Dose,” “Afternoon Dose,” and “Evening Dose.”

3.5.2. Methods to Minimize Bias

To minimize bias, the following measures will be taken:

- Investigational product allocation (KPI-121 0.25% ophthalmic suspension versus vehicle) will be randomized and masked to the sponsor, subjects, and select investigative staff.
- The randomization schedule will be generated by the randomization statistician (who is not on the project team) or designee and maintained in a secure and limited-access location separate from the study Investigator and members of the project team.

4. SELECTION OF SUBJECTS

4.1. SUBJECT INCLUSION CRITERIA

At Visit 1 and Visit 2, individuals of either gender or any race will be eligible for study participation if they:

1. Provide written informed consent and HIPAA authorization prior to any study-related procedures.
2. Are 18 years of age or older.
3. Are willing and able to follow instructions and can be present for the required study visits for the duration of the study. In addition, they must demonstrate:
 - a. Single-masked investigational product use compliance of at least 80% during the final week of the run-in phase AND
 - b. Diary completion compliance of at least 80% in the final week of the run-in phase.
4. Upon examination at **Visit 1 ONLY**, have **ALL 5** of the following criteria in the **same** or **both** eyes:

Severity Assessment.

- a. [Redacted]
- b. [Redacted]
- c. [Redacted]
- d. [Redacted]
- e. An unanesthetized Schirmer score [Redacted]

5. Are women of child bearing potential (WOCBP), who are not pregnant or lactating and not sexually active (i.e., abstinent) for 14 days prior to Visit 1 and are willing to remain so through 30 days following Visit 6 or the last administration of the investigational product or until completion of the subject's first menstrual cycle following the last administration of the investigational product, whichever period of time is longer. Alternatively, WOCBP who are not abstinent must have been using one of the following acceptable methods of birth control for the times specified:
 - a. IUD in place for at least 3 months prior to Visit 1 through Visit 6 or last administration of investigational product or until completion of the subject's first menstrual cycle following last administration of the investigational product, whichever period of time is longer.
 - b. Barrier method (condom or diaphragm) with spermicide for at least 3 months prior to Visit 1 through Visit 6 or last administration of the investigational product or until completion of the subject's first menstrual cycle following last administration of the investigational product, whichever period of time is longer.

- c. Stable hormonal contraceptive for at least 3 months prior to Visit 1 through Visit 6 or last administration of the investigational product or until completion of the subject's first menstrual cycle following administration of the investigational product, whichever period of time is longer.
NOTE: For Depo-Provera injection contraceptives, the statement regarding first menstrual cycle following administration of the investigational product is not applicable, as females receiving this form of contraception will not have menses.
- d. In a monogamous relationship with a surgically sterilized (i.e., vasectomized) partner for at least 6 months prior to Visit 1 through Visit 6 or last administration of the investigational product or until completion of the subject's first menstrual cycle following administration of the investigational product, whichever period of time is longer.

6. Are postmenopausal women, who have had no menstrual cycle for at least 1 year prior to Visit 1 or have undergone one of the following sterilization procedures at least 6 months prior to Visit 1:

- a. Bilateral tubal ligation
- b. Hysterectomy
- c. Hysterectomy with unilateral or bilateral oophorectomy.
- d. Bilateral oophorectomy

4.2. SUBJECT EXCLUSION CRITERIA

In order for subjects to be eligible at Visit 1 and Visit 2 they may not:

- 1. Have known hypersensitivity or contraindication to the investigational product(s) or their components.
- 2. Have used any of the following medications within 30 days prior to Screening (Visit 1) and for the duration of the study:
 - a. Ocular, inhaled, or intranasal corticosteroids
 - b. Ocular or oral NSAIDs with the exception of low dose aspirin (≤ 81 mg per day)
 - c. Topical ocular antibiotics
 - d. Topical ocular antihistamines or mast cell stabilizers
 - e. Oral antihistamines
 - f. Topical or nasal vasoconstrictors
- 3. Have used any of the following medications within 60 days prior to Screening (Visit 1) and for the duration of the study:
 - a. Topical cyclosporine (Restasis®)

- b. Any form of topical LE
4. Have altered oral dosing of the following within 30 days prior to Screening (Visit 1) or anticipate alteration of dosing during the study:
 - a. Tetracycline compounds (e.g., tetracycline, doxycycline, or minocycline)
 - b. Omega-3 or Omega-6 supplements
5. Have altered dosing of the following medications within 6 months prior to Screening (Visit 1) or anticipate alteration of dosing during the study:
 - a. Anticholinergics
 - b. Antidepressants
 - c. Isotretinoin
 - d. Oral corticosteroids
 - e. Systemic immunosuppressive agents
6. Be unwilling to abstain from the use of any topical ophthalmic medications at Visit 1 (Screening) and for the duration of the study, including:
 - a. Eyelash growth medications
 - b. Eye drops, gels, or artificial tears
7. Be unwilling to abstain from the use of TNF-blocking agents (e.g. etanercept, adalimumab, infliximab) at Visit 1 (Screening) and for the duration of the study.
8. Be currently receiving treatment for glaucoma, have history of or current glaucoma, or an IOP over 21mmHg at Visit 1 (Screening) or Visit 2 (Randomization).
9. Initiate or alter the use (if using upon entry) of oral contraceptives, or female hormone replacement therapy/supplementation within 48 hours prior to Visit 1 and for the duration of the study.
10. Be unwilling to abstain from wearing contact lenses for 14 days prior to Visit 1 and throughout the study.
11. Be monocular or have a BCVA, using corrective lenses if necessary, of +1.0 logMAR or worse as assessed by ETDRS.
12. Be unwilling to discontinue warm compress therapy, lid expression, or lid massage 14 days prior to Day 1 and for the duration of the study.
13. Have a diagnosis of:
 - a. Ongoing ocular infection
 - b. Moderate to severe pinguecula or pterygia
 - c. Stevens-Johnson Syndrome
 - d. Significant conjunctival scarring
 - e. Significant anterior blepharitis
 - f. Rosacea with corneal involvement.
 - g. Severe/serious ocular condition that in the judgment of the investigator could confound study assessments or limit compliance.

- h. Severe/serious systemic disease or uncontrolled medical condition that in the judgment of the investigator could confound study assessments or limit compliance.
- 14. Have concurrent acute hordeolum (stye) or chalazion.
- 15. Have significant anterior blepharitis, significant dandruff, or *Demodex follicularum* infestation.
- 16. Have obstruction of meibomian glands that present with no expressibility.
- 17. Have concurrent signs of moderate to severe chronic eyelid margin inflammation (moderate to severe eyelid margin telangiectasia and eyelid margin scarring) or lid structural abnormalities such as entropion, ectropion, trichiasis, or lash loss.
- 18. Have had ocular surgery in the past 90 days or require ocular surgery during the study.
- 19. Have active or have had an outbreak of herpetic keratitis within 1 year of Visit 1.
- 20. Have used eye make-up (e.g., eyeliner, mascara, eye shadow, eyelid glitter, eyelid concealer or base), eyelash curlers, eyelid glue, or false eyelashes at Visit 1 or are unwilling to discontinue the use of these products on the days of study visits.
- 21. Have permanent eyeliner.
- 22. Have a documented history of ocular allergies, which, in the judgment of the investigator, are likely to have an acute increase in severity due to the expected timing of exposure to the allergen to which the subject is sensitive. Subjects sensitive to seasonal allergens that are not expected to be present during the study are permitted.
- 23. Be an employee of the site that is directly involved in the management, administration, or support of this study or be an immediate family member of the same.
- 24. In the opinion of the Investigator or study coordinator, be unwilling or unable to comply with the study protocol or unable to successfully instill eye drops.

5. PROCEDURES

Written Informed Consent and HIPAA authorization will be obtained from all subjects prior to any study procedures being performed.

5.1. VISIT DESCRIPTIONS

5.1.1. Visit 1: 14 ± 1 Days Prior to Day 1 – Screening

After site staff obtains written informed consent and HIPAA authorization, each subject will be assigned a Subject Identification (ID) consisting of a 3-digit Investigator number plus a 3-digit Subject number. The Subject ID will be used as the primary subject identifier for the duration of the study. The following will be performed/assessed in order to determine initial eligibility for study participation:

- Non-ocular and ocular medical history
- Concomitant medication usage and medications taken during the 6 months prior to screening
- Urine pregnancy test (UPT) for WOCBP
- Subject-rated assessment of ocular discomfort
- [REDACTED]
- Investigator-rated assessment of signs
- Investigator-rated assessment of bulbar conjunctival hyperemia
- [REDACTED]
- TFBUT
- Corneal fluorescein staining
- Unanesthetized Schirmer Test evaluation
- BCVA
- Slit-lamp biomicroscopy
- IOP measurement
- Dilated ophthalmoscopy
- Review of inclusion and exclusion criteria to determine screening eligibility
- Dosing of run-in investigational product in clinic
- Dispensing of investigational product
- [REDACTED]

The first dose of single-masked investigational product will be taken in the clinic under the supervision of study personnel. Prior to administration, subjects will be instructed regarding proper instillation of investigational product. Since subjects will receive 1 dose of

investigational product in the clinic, they will self-administer at most 3 additional doses on the first day.

Instructions to subject:

- Dose run-in investigational product as instructed.
- [REDACTED]
- [REDACTED]
- Return for Visit 2 scheduled in 14 ± 1 days.

5.1.2. Visit 2: Day 1 (Randomization)

The randomization visit will occur 14 ± 1 day after Visit 1 (Screening). Subjects should dose run-in investigational product in both eyes QID until the Visit 2: Day 1 (Randomization).

The following will be performed/assessed at Visit 2:

- Use of any concomitant medications since the last visit
- Occurrence of any AEs since the last visit
- Subject-rated ocular discomfort assessment
- Investigator-rated assessment of signs
- Investigator-rated assessment of bulbar conjunctival hyperemia
- [REDACTED]
- TFBUT
- Corneal fluorescein staining
- BCVA
- Slit-lamp biomicroscopy
- IOP measurement
- [REDACTED]
- Unused run-in investigational product collected, counted, and compliance assessed
[REDACTED]
- Upon verification of subject eligibility ([Section 4](#) with the exception of Inclusion Criteria #4 and #7), randomization of appropriate subjects to receive QID dosing of either KPI-121 0.25% ophthalmic suspension or vehicle.
- Dosing of randomized investigational product in clinic
- Dispensing of randomized investigational product
- [REDACTED]

The first dose of double-masked investigational product will be taken in the clinic under the supervision of a designated dosing coordinator. This dosing coordinator, who is not responsible for study assessments, will also be required to dispense and retrieve investigational product to/from the subjects. Prior to dosing, subjects will be instructed regarding proper method for instillation of their assigned investigational product including but not limited to shaking the bottle prior to each instillation. Since subjects will receive 1 dose of investigational product in the clinic, they will self-administer at most 3 additional doses of investigational product on the first day.

Instructions to subject:

- Dose investigational product as instructed
- [REDACTED]
- [REDACTED]
- Return for Visit 3 on Day 8 ± 1 day.

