5.3. SUBJECT WITHDRAWAL AND/OR DISCONTINUATION

Any subject who wishes to discontinue investigational product use or withdraw from participation in the study for any reason is entitled to do so without obligation. The Investigator may also discontinue any subject from investigational product use or from study participation, if deemed necessary.

Investigational product use may be discontinued and any subject may be discontinued from study participation at any time during the study at the discretion of the Investigator or the sponsor for any reason including but not limited to:

1. Occurrence of any medical condition or circumstance that exposes the subject to substantial risk and/or does not allow the subject to adhere to the requirements of the protocol.
2. Any SAE, clinically significant AE, severe laboratory abnormality, intercurrent illness, or other medical condition that indicates to the Investigator that continued participation is not in the best interest of the subject.
3. Subject's decision to withdraw.
4. Any woman who becomes pregnant while participating in the study. Information on the pregnancy and outcome will be requested.
5. Subject's failure to comply with protocol requirements or study related procedures.
6. Termination of the study by the Sponsor, FDA, or other regulatory authorities.

In the event study discontinuation of a randomized subject is necessary, the Investigator should make every attempt to have the subject complete Visit 6 assessments as possible. If a non-serious AE is unresolved at the time of the subject's final study visit, an effort will be made to follow up until the AE is resolved or stabilized, the subject is lost to follow-up, or there is some other resolution of the event. The Investigator should make every attempt to follow all serious adverse events (SAEs) to resolution. The reason for premature discontinuation should be entered onto the Case Report Form (CRF) and recorded in the subject chart.

Subjects who withdraw from the study will not be replaced.

Additionally, the trial or parts of the trial may be discontinued by the sponsor or at the recommendation of the Investigator after consultation with Kala Pharmaceuticals, Inc. This may be based on a significant number of AEs of a similar nature that warrant such action.

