6. TREATMENT OF SUBJECTS

6.1. INVESTIGATIONAL PRODUCTS TO BE ADMINISTERED

All subjects meeting eligibility criteria at Visit 1 will receive 2 bottles of single-masked investigational product (vehicle). Subjects who continue to meet eligibility criteria at Visit 2 will be randomized to either KPI-121 0.25% ophthalmic suspension or vehicle. One kit of randomized investigational product containing 3 dropper bottles will be allocated to each subject at Visit 2. At Visit 2 (Day 1/Randomization), subjects will receive 2 bottles of double-masked investigational product (KPI-121 0.25% ophthalmic suspension or vehicle). At Visit 4 (Day 15 ± 1 day), subjects will receive 1 additional bottle of double-masked investigational product from the kit allocated. All bottles will be returned to the site at Visit 6 (Day 29 ± 1 day). The investigational product will be stored at the site in a secure area with limited access at controlled room temperature (15-25°C/59-77°F).

Subjects will be asked to administer investigational product QID. Prior to each instillation, subject will be instructed to shake the bottle. The subjects will record the time of administration of each dose of investigational product at the time of instillation ([Appendix 12](#)). Compliance with instillation of investigational product will be reviewed and assessed at each clinic visit.

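### Criterion 5 (not pregnant) must be re-verified at Visit 2, but no pregnancy test is scheduled there, so the only scheduled result before first possible active drug is 13 to 15 days old

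*Combined protocol and SAP*

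**What the plan says.** Section 4.1 opens its inclusion list with: "At Visit 1 and Visit 2, individuals of either gender or any race will be eligible for study participation if they". Criterion 5 covers WOCBP "who are not pregnant or lactating and not sexually active (i.e., abstinent) for 14 days prior to Visit 1", with continued abstinence afterwards. Women who are not abstinent must use a listed contraceptive method.

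Section 5.1.2 (Visit 2) makes randomisation follow a check of Section 4 eligibility "with the exception of Inclusion Criteria #4 and #7), randomization of appropriate subjects". The Synopsis and Section 3.5 carry the same two exemptions. The first randomised dose is then taken in clinic at that visit.

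The Visit 1 list in Section 5.1.1 includes "Urine pregnancy test (UPT) for WOCBP", and Section 5.1.6 lists the test again at Visit 6. It is not listed in Sections 5.1.2 to 5.1.5. The UPT row of Appendix 1 agrees, with marks at Visits 1 and 6 only. The Inclusion/Exclusion row is marked at Visits 1 and 2.

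Under Section 6.1, subjects eligible at Visit 1 "will receive 2 bottles of single-masked investigational product (vehicle"), so active drug cannot be given before Visit 2. Section 5.3 includes among its reasons for discontinuation: "Any woman who becomes pregnant while participating in the study".

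**The concern.** The protocol sets a pregnancy condition at two visits but schedules the test at only one of them, and that visit precedes vehicle rather than drug. The second scheduled test comes at the visit where dosing stops. At the moment when current knowledge of pregnancy status matters most, just before possible first exposure to loteprednol etabonate, no objective check is planned.

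What is at stake is subject safety and the quality of eligibility verification. The efficacy comparison is not affected. A pregnancy missed at Visit 1, or one that begins during the run-in, would meet no scheduled test before randomisation. The discontinuation provision in Section 5.3 would also have no scheduled test behind it while the woman is on randomised product.

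**Working it through.** The protocol states no figure for this interval, so there is none to reproduce. The check is a comparison of passages followed by date arithmetic.

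**Does criterion 5 have to be verified at Visit 2?**
- Section 4.1 applies the inclusion criteria at both visits.
- Section 5.1.2 exempts only #4 and #7. Criterion 5 is neither, so it must be verified.
- Only six inclusion criteria are listed, so the reference to #7 looks like a leftover cross-reference. It does not touch criterion 5.

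**Is a test scheduled at Visit 2?**

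| Source | Visit 1 | Visit 2 | Visits 3 to 5 | Visit 6 |
|---|---|---|---|---|
| Sections 5.1.1 to 5.1.6, pregnancy test | listed | not listed | not listed | listed |
| Appendix 1, UPT row | X | blank | blank | X |
| Appendix 1, Inclusion/Exclusion row | X | X | blank | blank |

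Redaction does not account for the gap. Some bullets in the Visit 2 list are blacked out, but the test is printed openly at Visits 1 and 6, and the UPT row of Appendix 1 is legible with only two marks.

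**How old is the result, and when is the next one?**

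Inputs:
- Visit 1 to Visit 2 (Section 5.1.2): "The randomization visit will occur 14 ± 1 day after Visit 1 (Screening"), which gives 13 to 15 days.
- Visit 6 (Section 5.1.6): Day 29 ± 1, counted from Visit 2 as Day 1. That is Day 28 to Day 30, or 28 − 1 = 27 to 30 − 1 = 29 days after Day 1.

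Results:
- Age of the only scheduled result at first possible active dose: **13 to 15 days**.
- First randomised dose to next scheduled test: **27 to 29 days**.
- Gap between the two scheduled tests: 13 + 27 = **40** to 15 + 29 = **44 days**.

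**Does the abstinence route close the gap?** It requires abstinence from 14 days before Visit 1, and the protocol states no contraception requirement for the time before that. For a woman on this route, the Visit 1 test may fall only 14 days after her last possible exposure. A Visit 2 test would fall at least 14 + 13 = 27 days after it. The protocol does not say how early its urine test detects pregnancy, so no detection rate is attached to either figure.

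**How does the protocol treat a comparable criterion?** Exclusion 8 rules out intraocular pressure above 21 mmHg at Visit 1 or Visit 2, and the pressure is measured at both visits (Sections 5.1.1 and 5.1.2). Pregnancy status must also hold at both visits but is tested at one.

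**The case against.** The strongest reply is that the plan is internally consistent. The visit lists and Appendix 1 agree with each other, and no passage says that verification at Visit 2 must be by test. Other Visit 2 criteria, such as prior medication, contact lens wear and contraception, are confirmed by history, and a site could do the same here. That stands. A reader might infer that the sections contradict each other, or that criterion 5 cannot be enforced. The documents do not support either: the rule can be applied, only without a second objective check.

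The protocol also has real safeguards. Criterion 5 admits WOCBP only if they are abstinent from 14 days before Visit 1 onwards or use a listed method. An IUD, barrier with spermicide, or hormonal contraception must have been used for at least 3 months before Visit 1, and a relationship with a vasectomised partner must have lasted at least 6 months. Adverse events and medications are queried at every visit, unscheduled visits are provided for, and Section 5.3 allows discontinuation at any time. About half of randomised subjects receive vehicle. These points lower the probability and the likely duration of exposure, and they stand. They do not establish status before the first dose.

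A reader might go on to infer that an affected woman would take active drug for the entire randomised period. That does not follow. She may be on vehicle, and a pregnancy recognised by other means could be acted on before Visit 6.

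A reader might also object to the short list in Section 5.1.8, which omits the test at early termination. That section first asks for every attempt at all Visit 6 assessments, which include the test, and the short list applies only when this is not feasible. It is not part of this point.

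Finally, the documents give no reproductive-risk figure for topical loteprednol. Sections 1 and 1.2 refer risks and toxicology to the Investigator's Brochure, which is not among the documents reviewed. The size of any harm therefore cannot be stated.

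**Conclusion.** The point holds as a gap in verification, not as a contradiction. The protocol requires WOCBP to be not pregnant at Visit 2 and makes randomisation conditional on checking this, but it schedules no test there. The only scheduled result at first possible corticosteroid exposure is 13 to 15 days old, the next comes 27 to 29 days later, and 40 to 44 days separate the two. A woman whose pregnancy was not detected at Visit 1 could receive active drug until it is otherwise recognised.

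The intervals rest only on the stated visit windows. The number of exposed pregnancies cannot be estimated, because the documents give no WOCBP share, no pregnancy rate under the contraception rules and no detection limit for the test. A reader might take the number of WOCBP in the active arm as the scale of harm. That would count women without a second test, not exposed pregnancies, which would be a small fraction of them given the safeguards. The case for change is that a safety check the protocol already relies on can be put at the right visit for very little.

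**What to change.** Reconcile Sections 4.1 and 5.1.2 with Appendix 1:
- Add the existing pregnancy test for WOCBP to the Visit 2 list in Section 5.1.2, ahead of the eligibility verification step.
- Mark Visit 2 in the UPT row of Appendix 1.

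The protocol's own criterion 5 would then be checked by test before randomisation. The change alters no dose, rescue or stopping provision.

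The cost is a protocol amendment, one urine test per WOCBP at a visit that already takes place, and an occasional extra failure at Visit 2. Sites already run the test at Visits 1 and 6, so no new staff or visit is needed.
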